6.2.3. Baseline Age

Calculation of subject’s age in years is based on the date of informed consent, using the following formula: Age (year) = FLOOR ([date of informed consent – date of birth] / 365.25), where the FLOOR () function returns the integer part of the result.

6.2.4. Week 52/ET Assessments

Subjects who discontinue study drug or who are withdrawn from the study are required to return for an EOS or ET visit. The muscle strength tests, pulmonary function tests, motor function tests, PRO assessments, and pharmacodynamic endpoints (Hex4 and CK) performed at the ET visit will be used as the final values at the Week 52 visit for statistical analysis. The 6MWT is to be performed twice at the Week 52/ET visit, and the average of the 2 test values will be used as the final value at Week 52 for statistical analysis.

Note: As a result of the COVID-19 related policies and restrictions, the Week 52 visit (and/or the ET/EOS visit) may be delayed. Even if that happens, the delayed visit assessments will still be used for analyses. The make-up assessments at Week 52 will be used as the Week 52 results. In addition, some subjects were only able to have 1 assessment of 6MWD at Week 52. For these subjects, the single assessment will still be used as the Week 52 value.

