6.1.4.1. ITT-OBS

The ITT-OBS is the ITT population using all available, observed data without imputation for missing post-baseline data. That is, missing data at Week 52 and at other visits are not replaced.

The ITT-OBS population is identical to the ITT population as defined above. The mixed-effect model for repeated measures (MMRM) analysis will be performed on the ITT-OBS population.

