6.1.4.2. ITT-LOCF

The ITT-LOCF is the ITT population with missing data replaced with the last available value from post-baseline results. That is, the LOCF replaces missing data at Weeks 26, 38, and 52 with the last available endpoint value. Where applicable, the observed baseline result will be used to replace a missing post-baseline result at the Week 12 visit. Imputed baseline value cannot be used to replace missing Week 12 result. The missing value at Week 52 is replaced with the last

available value from the subject in the study. This can be the value from the early termination (ET)/end of study (EOS) visit if available. If not available, the last available value from prior post-baseline visits (Week 38, Week 26, or Week 12, whichever is available) will be used to replace the missing value at Week 52.

Example for visits earlier than Week 52: Suppose the subject only missed the assessment at Week 12 but had assessments at some other visits after Week 12 (ie, Week 26 and/or Week 38 and/or Week 52). Then the missing assessment at Week 12 is replaced with the last available value on/prior to Week 12 (eg, the observed baseline value). If the subject missed the Week 12 visit due to discontinuation/withdrawal from the study and had follow-up assessments at the ET/EOS visit, then the last available value from the ET/EOS visit will be used to replace the missing Week 12 value. This EOS value is then carried forward to replace missing values at Weeks 26, 38, and 52 as the subject had withdrawn from the study since Week 12.

Note: The observed baseline result can only be used to replace missing data at Week 12, where applicable (ie, if the subject has other post-baseline data). It will not be carried forward to replace missing values at Week 26, 36 or 52. In addition, imputed baseline values cannot be used to replace missing post-baseline values.

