6.1.7. Completers

The Completers population consists of subjects who completed the Week 52 visit and have both 6MWD and FVC assessments at the Week 52 visit (including make-up assessments or delayed visits). Subjects who completed the Week 52 visit and were able to do only 1 6MWT (instead of 2) at Week 52 will still be considered as completers. This population will be used for subject accounting purposes.

A subject who withdraws/discontinues from the study and returns for the end of study or early termination visit is not a completer and does not belong in the Completers population.

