6.2.6. Analysis Visit Windows

6.2.6.1. Visit Windows

Analysis visit windows will be used for all by-visit analyses, as provided for in Table 3 and Table 4.

Table 3: Visit Windows for Functional Assessments, PROs, ECG, and CPE (as applicable)

Visit	Week	Target Day	Analysis Visit Window
Visit 1	Week -2 ^a	Day -15/-14	Screening/Baseline for efficacy
Visit 1.10 ^b	< Week 0	Day -10	Randomization
Visit 6	Week 12	Day 85	Day 2 – 134
Visit 7	Week 26	Day 183	Day 135 – 225
Visit 8	Week 38	Day 267	Day 226 – 316
Visit 9 (EOS/ET)	Week 52	Day 365	> Day 316
Visit 10 (F/U) ^c	Week X.10	N/A	N/A

Abbreviations: AE = adverse event; CPE = complete physical exam; ECG = electrocardiogram; EOS = end of study; ET = early termination; F/U = follow-up; IRT = Interactive Response Technology; N/A = not applicable; PRO = Patient-reported outcome

^a Denotes Day -15/-14 in the screening period.

^b Denotes the randomization day. Randomization is carried out via the IRT system and subjects do not need to be present. Hence, ‘randomization day’ is not a scheduled visit in the study protocol. Using the ‘Visit 1.10’ designation can help with data programming for analysis purposes.

^c Denotes follow-up visits occurring at Week X.10 (AEs and concomitant medications are to be collected up to 30 days after last dose date).

Table 4: Visit Windows for Vital Signs, Lab Measurements, and BPE (as applicable)

Visit	Week	Target Day	Analysis Visit Window
Visit 1	Week -2 ^a	Day -15/-14	Screening/Baseline for efficacy
Visit 1.10 ^b	< Week 0	Day -10	Randomization
Visit 2	Week 0 ^c	Day 1	Baseline for safety
Visit 3	Week 2	Day 15	Day 2 – 22
Visit 4	Week 4	Day 29	Day 23 – 36
Visit 5	Week 6	Day 43	Day 37 – 64
Visit 6	Week 12	Day 85	Day 65 – 134
Visit 7	Week 26	Day 183	Day 135 – 225
Visit 8	Week 38	Day 267	Day 226 – 316
Visit 9 (EOS/ET)	Week 52	Day 365	> Day 316
Visit 10 (F/U) ^d	Week X.10	N/A	N/A

Abbreviations: AE = adverse event; BPE = brief physical exam; EOS = end of study; ET = early termination; F/U = follow-up; IRT = Interactive Response Technology; N/A = not applicable; PRO = patient-reported outcome

^a Denotes Day -15/-14 in the screening period.

^b Denotes the randomization day. Randomization is carried out via the IRT system and subjects do not need to be present. Hence, ‘randomization day’ is not a scheduled visit in the study protocol. Using the ‘Visit 1.10’ designation can help with data programming for analysis purposes.

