6.2.7. Multiple Assessments in a Visit Window

6.2.7.1. For Efficacy Data

In general, for all post-baseline efficacy and other functional by-visit analyses, if multiple assessments (from both scheduled and unscheduled visits) occur in the same visit window, the visit dates should first be examined to see if they are part of the COVID-19 related delayed visits or make-up assessments that require visit windows to be adjusted or remapped (as discussed in Section 6.2.6.2) in order for the data to be in the appropriate study visits.

- If they are part of COVID-19 related delayed visits or make-up assessments, then the assessments should be handled in accordance with the handling of delayed visits and make-up assessments in Section 6.2.4 and the visit window remapping described in Section 6.2.6.2.
- If they are not part of COVID-19 related delayed visits or make-up assessments that require visit window adjustment per Section 6.2.4 and Section 6.2.6.2, then the usual visit window rules apply.

That is, if they are not COVID-19 related (or even if they are COVID-19 related but do not require any visit window adjustment or remapping), then for multiple assessments in the same visit window, the value closest to the planned target visit day will be used for analysis at that visit. If two assessments are equidistant from the target day, or if two assessments occur on the exact same day but at different times, the last value in chronological order will be used.

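### SAP 6.2.4 assigns early-termination results to Week 52 with no population or study-day limit; read literally, this conflicts with the visit windows and the ITT-OBS no-replacement rule

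*SAP*

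**What the plan says.** SAP 6.2.4 opens with subjects who stop study drug or are withdrawn. Their strength, pulmonary, motor, patient-reported and pharmacodynamic results "performed at the ET visit will be used as the final values at the Week 52 visit for statistical analysis". For the 6MWT, two walks are done "at the Week 52/ET visit, and the average of the 2 test values will be used as the final value at Week 52". The section sets no population and no study-day limit. Protocol 12.2.6 has the same unrestricted averaging rule for 6MWD.

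Other SAP sections handle the same data differently:

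- **6.2.6.1:** "Analysis visit windows will be used for all by-visit analyses, as provided for in Table 3 and Table 4". In Table 3, Days 2–134 are Week 12, Days 135–225 are Week 26, Days 226–316 are Week 38, and later days are Week 52. The Week 52 row carries the label EOS/ET.
- **6.2.7.1:** when several assessments share a window, 6.2.4 is invoked only for COVID-19 delayed or make-up visits. For assessments that do not require "visit window adjustment per Section 6.2.4 and Section 6.2.6.2, then the usual visit window rules apply".
- **6.1.4.1 and 6.3.2:** in ITT-OBS, "missing data at Week 52 and at other visits are not replaced".
- **6.1.4.2 and 6.3.2:** replacing a missing Week 52 value from the ET visit belongs to ITT-LOCF: "This can be the value from the early termination (ET)/end of study (EOS) visit if available". The worked example fills the earlier visit first: if Week 12 was missed through withdrawal, "then the last available value from the ET/EOS visit will be used to replace the missing Week 12 value", and that value is carried on.
- **6.1.7:** "A subject who withdraws/discontinues from the study and returns for the end of study or early termination visit is not a completer".
- **6.4, Table 5:** in ITT-OBS the value observed at discontinuation is used, with no visit named, and later data are missing under MAR.

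The primary 6MWD analysis (8.5.1) is an MMRM on ITT-OBS.

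**The concern.** The no-replacement rule protects Week 52 only while Week 52 is missing. Section 6.2.4 is a derivation rule. If a programmer applies it literally, an ET walk on, say, Day 150 becomes an observed Week 52 value before the question of missingness arises. The primary MMRM then contains what is in effect a carried-forward walk, although the SAP describes that model as using observed data without imputation. The supportive ITT-OBS MMRMs of the key secondary endpoints (8.5.1.1, 8.6) and the ITT-OBS ANCOVA of % predicted 6MWD (8.5.1.2) would be affected in the same way.

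Two further consequences follow from a literal reading.

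- The control-based imputation in 8.2, which is used to judge MAR, acts on missing values, so it would have fewer Week 52 values to work on.
- The Week 26 6MWD endpoint is analysed by ANCOVA on ITT-LOCF. It would lose an ET walk that falls in the Week 26 window.

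Fixing the mapping in advance also removes a choice between two primary datasets after unblinding.

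**Working it through.** **1. The plan's figures.** With 66 vs 33 subjects, effect size 0.7 and one-sided 0.025 (SAP 4.3), the noncentral t with 97 df gives 90.2% power, matching the stated 90%. Also 99 / 0.90 = 110 randomised, so 10% dropout is 11 subjects. The point disputes none of these.

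**2. How often the readings differ.** They differ for any ET visit on Days 2–316. That is 315 of the 364 days from Day 2 to Day 365, or 86.5%. If 11 withdrawals were spread evenly over those days and all had an ET walk (both assumptions), 11 × 315/364 ≈ 9.5 subjects would gain a Week 52 value that Table 3 leaves missing.

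**3. One subject, ET walk on Day 150, no scheduled Week 26 walk.**

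| | Literal 6.2.4 | Table 3 windows |
|---|---|---|
| ITT-OBS | Week 52 observed; Week 26 missing | Week 26 observed; Weeks 38 and 52 missing |
| ITT-LOCF, Week 52 | ET value | ET value, carried forward |
| ITT-LOCF, Week 26 | filled from Week 12 | ET value |

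The readings agree for Week 52 in ITT-LOCF, but not for Week 26.

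**4. Size in the primary MMRM.** Simulation, 6,000 replicates per scenario, 73 vs 37 subjects, each dataset analysed under both readings with a four-visit unstructured-covariance model. From SAP Appendix 1: a true effect of 20, 30 or 40 m, with Week 52 SD = effect/0.7 (28.6, 42.9, 57.1 m). Assumed, not in the documents: random intercept, slope and residual SDs in ratio 30:30:20; equal withdrawal in both arms, uniform over Days 30–316 unless stated; the share of withdrawals with an ET walk; a flat control course; no baseline covariates.

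Mean shift in the Week 52 difference, literal minus windows (m):

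| Scenario | 20 m | 30 m | 40 m |
|---|---|---|---|
| 10% withdraw, linear gain, all have ET walk | −1.0 | −1.5 | −2.0 |
| same, withdrawal spread to Day 364 | −0.9 | −1.3 | −1.7 |
| same as first row, half have ET walk | −0.5 | −0.8 | −1.1 |
| 10%, all gain reached by Day 183, all have ET walk | −0.4 | −0.5 | −0.8 |
| 5%, linear, all have ET walk | −0.5 | −0.7 | −1.0 |
| 5%, gain by Day 183, all have ET walk | −0.2 | −0.3 | −0.4 |
| 5%, gain by Day 183, half have ET walk | −0.1 | −0.1 | −0.2 |
| Model SE | 5.9 | 8.8 | 11.8 |

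Hand check of the first row at 30 m, using the mean withdrawal day (30 + 316)/2 = 173: 0.10 × (1 − 173/365) × 30 = 1.6 m, against 1.5 m simulated. There the estimates are 28.5 m (literal) and 30.0 m (windows), with power 91.3% and 92.3%. Over all 21 cells power differs by at most 1.1 points, and the significance result differs in 0.7–2.5% of simulated trials. With no true effect the mean shift is 0.0 m.

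A smaller simulation (300 replicates, within-subject correlation 0.6, 30 m, linear, all with an ET walk) gave 28.4 vs 29.8 m at 10% withdrawal and 29.3 vs 30.1 m at 5%. With 15% active and 3% control withdrawal it gave 27.3 vs 29.8 m. The documents give no reason to expect that imbalance, so it is not counted in the range.

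**5. The 8.2 check** (10% withdrawal, linear; each missing Week 52 change replaced by the mean of 15 control draws). Under the windows about 11 values are imputed and the estimate moves by −2.0/−2.9/−3.9 m (hand check at 30 m: 0.10 × 30 = 3.0 m). Under the literal reading with an ET walk for every withdrawal, none are imputed and it moves by 0.0 m. With half having an ET walk, about 5.5 are imputed and it moves by −1.0/−1.5/−1.9 m.

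**The case against.** The strongest reply is that the SAP already settles the matter. The windows cover all by-visit analyses, ITT-OBS is unreplaced, ET replacement is tied to ITT-LOCF, and Table 5 makes data after discontinuation missing. The sentence that plainly turns ET results into Week 52 results does not list the 6MWT. The 6MWT has its own sentence, which reads naturally as a rule for averaging two walks at a visit whose name happens to be Week 52/ET. The endpoints that are listed have their main analyses mostly on ITT-LOCF, where the rule fits at Week 52.

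Most of this stands as evidence of intent. It does not close the gap. The no-replacement rule does not bite once 6.2.4 has filled Week 52. The return to usual windows in 6.2.7.1 is written for several assessments in one window, not for a lone ET visit. The EOS/ET label in Table 3 and the unnamed visit in Table 5 both invite the literal reading. Protocol 12.2.6 cannot decide it, because its wording is equally open and SAP Section 2 says the SAP supersedes the protocol.

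A reader might also infer that the MAR check in 8.2 would pass by construction. That goes too far. Section 8.2 gives Week 52 only as an example. The check is empty there only if every withdrawal has an ET walk and no other Week 52 value is missing, and 8.2 itself expects some subjects to be unassessable because of COVID-19. It also looks at the amount, reasons and balance of missing data, and its criterion is same direction and similar conclusions, which a movement of 2–4 m would seldom alter.

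**Conclusion.** The point holds as a drafting conflict and is minor. Section 6.2.4 as written permits an ET walk on or before Day 316 to be an observed Week 52 value in the primary MMRM, against the intent of the other sections. The likely size is about 0.1 to 2 m against a standard error of about 6 to 12 m. That rests on the assumed variance ratio, withdrawal timing, ET attendance, flat control course and equal withdrawal, and on a model without the planned covariates. The effect is nil if nobody has an ET visit by Day 316.

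Two stronger inferences are not supported. One is that the SAP plans a carried-forward primary analysis: its sections taken together say the opposite, and the ITT-LOCF ANCOVA, the PP1 exclusions and the disposition tables keep withdrawals visible. The other is that 6.2.4 is right as it stands for every ITT-LOCF analysis: it agrees with the windows at Week 52, but not for the Week 26 6MWD endpoint.

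**What to change.** Before database lock:

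1. Keep the averaging of the two walks (or use of the single walk) in 6.2.4 for all populations.
2. State that an ET assessment goes to the Table 3 window containing its study day in every population, with 6.2.7.1 for multiple values and 6.2.6.2 for COVID-19 delayed or make-up visits.
3. State that in ITT-OBS Week 52 stays missing unless the ET visit is after Day 316. Only in ITT-LOCF is the ET value then carried forward under 6.1.4.2 to later missing visits, including Week 52. An ET walk on Days 135–225 then counts at Week 26 for the Week 26 6MWD endpoint.
4. Add a cross-reference to this rule in Table 5 and at the EOS/ET label in Table 3.

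The cost is a few sentences, the cross-references and one derivation flag. No new data or analysis is needed, and the sample size and power are unchanged.

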6.2.5. Change and Percent Change from Baseline

Change from baseline is calculated as:

$$\text{Value at a visit} - \text{Baseline value.}$$

Percent change from baseline is calculated as:

$$100 * (\text{Value at a visit} - \text{Baseline value}) / \text{Baseline value.}$$

6.2.6. Analysis Visit Windows

6.2.6.1. Visit Windows

Analysis visit windows will be used for all by-visit analyses, as provided for in Table 3 and Table 4.

Table 3: Visit Windows for Functional Assessments, PROs, ECG, and CPE (as applicable)

Visit	Week	Target Day	Analysis Visit Window
Visit 1	Week -2 ^a	Day -15/-14	Screening/Baseline for efficacy
Visit 1.10 ^b	< Week 0	Day -10	Randomization
Visit 6	Week 12	Day 85	Day 2 – 134
Visit 7	Week 26	Day 183	Day 135 – 225
Visit 8	Week 38	Day 267	Day 226 – 316
Visit 9 (EOS/ET)	Week 52	Day 365	> Day 316
Visit 10 (F/U) ^c	Week X.10	N/A	N/A

Abbreviations: AE = adverse event; CPE = complete physical exam; ECG = electrocardiogram; EOS = end of study; ET = early termination; F/U = follow-up; IRT = Interactive Response Technology; N/A = not applicable; PRO = Patient-reported outcome

^a Denotes Day -15/-14 in the screening period.

^b Denotes the randomization day. Randomization is carried out via the IRT system and subjects do not need to be present. Hence, ‘randomization day’ is not a scheduled visit in the study protocol. Using the ‘Visit 1.10’ designation can help with data programming for analysis purposes.

^c Denotes follow-up visits occurring at Week X.10 (AEs and concomitant medications are to be collected up to 30 days after last dose date).

Table 4: Visit Windows for Vital Signs, Lab Measurements, and BPE (as applicable)

Visit	Week	Target Day	Analysis Visit Window
Visit 1	Week -2 ^a	Day -15/-14	Screening/Baseline for efficacy
Visit 1.10 ^b	< Week 0	Day -10	Randomization
Visit 2	Week 0 ^c	Day 1	Baseline for safety
Visit 3	Week 2	Day 15	Day 2 – 22
Visit 4	Week 4	Day 29	Day 23 – 36
Visit 5	Week 6	Day 43	Day 37 – 64
Visit 6	Week 12	Day 85	Day 65 – 134
Visit 7	Week 26	Day 183	Day 135 – 225
Visit 8	Week 38	Day 267	Day 226 – 316
Visit 9 (EOS/ET)	Week 52	Day 365	> Day 316
Visit 10 (F/U) ^d	Week X.10	N/A	N/A

Abbreviations: AE = adverse event; BPE = brief physical exam; EOS = end of study; ET = early termination; F/U = follow-up; IRT = Interactive Response Technology; N/A = not applicable; PRO = patient-reported outcome

^a Denotes Day -15/-14 in the screening period.

^b Denotes the randomization day. Randomization is carried out via the IRT system and subjects do not need to be present. Hence, ‘randomization day’ is not a scheduled visit in the study protocol. Using the ‘Visit 1.10’ designation can help with data programming for analysis purposes.

^c Denotes study visit Day 1, at which baseline safety assessments are performed.

^d Denotes follow-up visits occurring at Week X.10 (AEs and concomitant medications are to be collected up to 30 days after last dose date).

6.2.6.2. Impact of COVID-19 on the Visit Windows

Due to the COVID-19 related policies and restrictions, sites were allowed to perform make-up assessments at a later date when feasible. This resulted in some delayed visits, and some of this may appear in the Study Data Tabulation Model (SDTM) datasets as unscheduled visits or multiple assessments at some specified visits.

Delayed visits and make-up assessments that go beyond the stated visit windows will be remapped to the planned study visit. For example, the visit window for Week 26 is Day 135 to Day 225, and the window for Week 38 is Day 226 to Day 316. Suppose a subject had a COVID-19 related situation leading to a delay in the Week 26 assessment such that the delayed visit / make-up assessment for Week 26 occurs on Day 261 (which is 36 days outside of the planned visit window for Week 26, and it’s inside the Week 38 visit window), followed by the Week 38 assessment on Day 300 (which is right within the Week 38 visit window). Here, the delayed assessment occurring on Day 261 will be remapped to the Week 26 visit (which was the intended visit).

6.2.7. Multiple Assessments in a Visit Window

6.2.7.1. For Efficacy Data

In general, for all post-baseline efficacy and other functional by-visit analyses, if multiple assessments (from both scheduled and unscheduled visits) occur in the same visit window, the visit dates should first be examined to see if they are part of the COVID-19 related delayed visits or make-up assessments that require visit windows to be adjusted or remapped (as discussed in Section 6.2.6.2) in order for the data to be in the appropriate study visits.

- If they are part of COVID-19 related delayed visits or make-up assessments, then the assessments should be handled in accordance with the handling of delayed visits and make-up assessments in Section 6.2.4 and the visit window remapping described in Section 6.2.6.2.
- If they are not part of COVID-19 related delayed visits or make-up assessments that require visit window adjustment per Section 6.2.4 and Section 6.2.6.2, then the usual visit window rules apply.

That is, if they are not COVID-19 related (or even if they are COVID-19 related but do not require any visit window adjustment or remapping), then for multiple assessments in the same visit window, the value closest to the planned target visit day will be used for analysis at that visit. If two assessments are equidistant from the target day, or if two assessments occur on the exact same day but at different times, the last value in chronological order will be used.

6.2.7.2. For Safety Data

For all post-baseline safety by-visit analyses, if multiple assessments (from both scheduled and unscheduled visits) occur in the same visit window, the value closest to the planned target visit day will be used for that visit (unless these are COVID-19 related delayed visits for which visit window adjustment or remapping is required). If two assessments are equidistant from the target day or occur on the same day but at different times, the last assessment in chronological order will be used (unless these are COVID-19 related delayed visits for which visit window adjustment or remapping is required).

Note: See Section 6.2.6.2 regarding the handling of the impact of COVID-19 related delayed visits and assessments on the analysis visit windows.

